HYPOTHESIS 4: Compared to placebo, CNTX-6970 300mg BID will result in more improvement with respect to (a) Staircase-Evoked Pain Assessment, (b) Serum and synovial fluid levels of chemokines and cytokines; and (c) Synovial monocyte chemoattractant protein-1/CCR-2 receptor binding inhibition in blood and synovial fluid.

The Staircase-Evoked Pain Assessment will be assessed at Baseline and each in-person study visit through Week 24 (Week 3, 6, 9, 12, 15, 18, 21, and 24/ET visits).

Hypothesis 4 will be tested with the same approach as for testing the hypotheses under Aim 3.

K.3. Exploratory analyses

Aim 6. If CNTX-6970 is more effective than placebo, evaluate the following characteristics of its effect: (a) onset of action; (b) carryover effect after treatment discontinuation.

We will study the change of symptoms over time using a time trend in our statistical models within each of the 6-week treatment periods to model the weekly WOMAC-A measure.

Under this aim, the interest is not in hypothesis testing, but rather in understanding the progression and magnitude of onset of action and the carryover effects of the CNTX-6970 compound. This approach will allow an elucidation of the nature of action of the compound.

Aim 7. Identify biomarkers related to pain from OA of the knee, course of the disease, and response to treatment with CNTX-6970.

Statisticians on the study team have published methods for analysis of complex multimodal data, such as EEG and brain imaging for developing optimal treatment decision (e.g., Ciarleglio et al, 2018; Jiang et al, 2020; Park et al, 2020a; Park et al, 2020b; Petkova et al, 2020), one of the objectives of precision medicine. Although this previous work has been primarily motivated by mental health research (e.g., depression), the methodologies developed apply equally to pain and other medical conditions. As necessary, new methodologies will be developed for the joint analysis of outcome measures.

The results of these investigations are expected to be features (for example, the variability of pain across days) or combinations of features that constitute biosignatures for specific response to CNTX-6970, placebo response, or non-specific response to both an active agent and placebo. For all indices and estimates, we will perform extensive internal cross-validation. All results from these discovery analyses will be reported as exploratory and subject to independent validation. The interpretation of the results will also be in the context of all analyses that were performed, and will emphasize the discovery nature of the work.

Aim 8: Explore sociodemographic and clinical predictors of response to CNTX-6970.

The rich data collection will allow for exploration of the relationship between treatment with CNTX-6970 and placebo, and sociodemographic and clinical covariates. No hypotheses will be tested under this aim. Rather various research questions will be addressed, such as:

Q1: Do women show a greater reduction in pain ratings following CNTX-6970 compared to placebo, relative to men?

Q2: Do patients with high levels of psychological distress show a greater reduction of pain with CNTX-6970, relative to patients who do not have high levels of psychological distress?

K.4. Sample Size

The sample size for this study was determined based on the primary efficacy aim to detect a significant effect of each dose of CNTX-6970 compared to placebo in the multi-period crossover design model. Power was computed for effect sizes ranging from 0.25 to 0.50 using Monte Carlo simulation. Data were simulated from multi-period crossover models with block, period, and carryover effects, and varying within and between subject variability. Although carryover effects can be efficiently isolated and estimated in the analysis stage by using mixed-effects models, power for the primary hypothesis was computed using only WOMAC-A assessed during the last 2 of 6 weeks per treatment period to minimize carryover effects. The power of the test depends on

the relationship of the between-subject variability to the within-subject variability. In general, the between-subject variability is larger than the within-subject variability, but we investigated a range of Between/Within (B/W) variance ratios (5/1, 2/1). With a total sample size of $n=55$, there will be more than adequate power for the study using a two-sided Type I error rate of $\alpha=0.05$. A power analysis was conducted with $n=50$ and the power to detect an effect size (for an active treatment vs. placebo) of Cohen's $d=0.35$ is approximately 95% when the ratio B/W=2/1. Assuming a 15% early termination rate during each of the 4 periods will yield a sample size of $n=26$ with complete observations at all treatment periods for this simulation. If we conservatively assume that only subjects with complete data will be analyzed, the corresponding power with $n=26$ is approximately 81%. Because we will use all available data from all enrolled subjects in the analysis, the actual power in the case of 15% early termination rate per treatment period will be larger than 81%, and anywhere between 81% and 95%. If the ratio B/W is larger than 2, say B/W=3, 4 or 5, the power for detecting the treatment effects is much larger. For example, with only 26 patients, if B/W=5, the power to detect an effect of magnitude Cohen's $d=0.35$ is 0.96. Note that the reported test-retest reliability of the WOMAC-A measure is 0.86, which corresponds to a B/W=7.

[figure not shown]

Figure 2: Power versus Cohen's d effect size. B/W indicates the ratio of between-subject to within-subject variance of the WOMAC-A measure. Assuming that only data from completers will be used in the analysis gives a lower bound of the power that can be achieved for the given range of effect sizes.

■ PUBLICATION POLICY

See EPPIC-Net Publication Policy.

■ REFERENCES

Appendix I: BLINDED INFORMATION

Available upon request.

Appendix II: Cytokines & Chemokines (from the Inflammation MAP Multiplex panel):

Adiponectin	Interleukin-23
Alpha-1-Antitrypsin	Interleukin-3
Alpha-2-Macroglobulin	Interleukin-4
Apolipoprotein(a)	Interleukin-5
Beta-2-Microglobulin	Interleukin-6
Brain-Derived Neurotrophic Factor	Interleukin-7
C-Reactive Protein	Interleukin-8
Complement C3	Macrophage Inflammatory Protein-1 alpha
EN-RAGE	Macrophage Inflammatory Protein-1 beta
Eotaxin-1	Matrix Metalloproteinase-3
Factor VII	Matrix Metalloproteinase-9
Ferritin	Monocyte Chemotactic Protein 1
Fibrinogen	Myoglobin
Granulocyte-Macrophage Colony-Stimulating Factor	Plasminogen Activator Inhibitor 1
Haptoglobin	Pulmonary and Activation-Regulated Chemokine
Immunoglobulin A	Serum Amyloid P-Component
Immunoglobulin M	Stem Cell Factor
Intercellular Adhesion Molecule 1	T-Cell-Specific Protein RANTES
Interferon gamma	Thyroxine-Binding Globulin
Interleukin-1 alpha	Tissue Inhibitor of Metalloproteinases 1
Interleukin-1 beta	Tumor Necrosis Factor alpha
Interleukin-1 receptor antagonist	Tumor Necrosis Factor beta
Interleukin-10	Tumor necrosis factor receptor 2
Interleukin-12 Subunit p40	Vascular Cell Adhesion Molecule-1
Interleukin-12 Subunit p70	Vascular Endothelial Growth Factor
Interleukin-17	Vitamin D-Binding Protein
Interleukin-18	von Willebrand Factor
Interleukin-2	

Appendix III: Concomitant Medications

Subjects who take prohibited concomitant medications during the trial will be discontinued, unless the discontinuation presents an unacceptable medical risk. The justification to allow the subject to continue in the trial will be made by the Sponsor with medical input from a site investigator (PI, clinical Sub-I), and will be documented. Whether or not the participant is allowed to remain in the trial, this will be reported as a major protocol deviation and not a waiver.

The table below lists prohibitions and restrictions by medication class, including representative medications within class. Medications within each class include, but are not limited to, examples listed in this table. Any questions regarding prohibited and restricted medications should be discussed with the Medical Monitor or appropriate designee.

The direct FDA link for all CYP2C9, CYP3A4, and P-GP interactions is: [Drug Development and Drug Interactions | Table of Substrates, Inhibitors and Inducers | FDA](#)

Drug Name or Class	Episodic Use (PRN)	Chronic Use	Restrictions/Comments
Analgesics	Y	Y	
Acetaminophen, opioids, and select anticonvulsants are allowed as a rescue medication (as described in the respective sections). Other analgesics as specified below:
 
Continuous use of one of the following medications prescribed for pain is allowed: tramadol, gabapentin, duloxetine, pregabalin, milnacipran, or tricyclic antidepressants. Use must be chronic for at least 12 weeks and at a stable dose for at least 4 weeks before Screening.
 
Intermittent use of opioids is allowed if use is ongoing for at least 4 weeks before Screening, and at a frequency no more than 4 days/week, and the opioid is not taken within 24 hours of a study visit.
 
As needed use of acetaminophen is allowed.
 
Continuous use of medical marijuana (or equivalent) that is chronic for at least 12 weeks and at a stable dose for 4 weeks is allowed.
 
Continuous use of topical creams (includes CBD topicals) is allowed if use is chronic and stable for at least 12 weeks.
 
Intermittent use of topical creams is allowed if at a frequency of no more than 4 days/week.
 
Other analgesics (for example, NSAIDS) are not allowed.

Drug Name or Class	Episodic Use (PRN)	Chronic Use	Restrictions/Comments
Anesthetics, general	Y	—	If procedures requiring general anesthesia are to occur/have occurred, please contact MGH CTNI to report the medical condition(s).
Anesthetics, local	Y	N	—
Anorexics	N	N	—
Antacids	Y	Y	—
Antiacne	Y	Y	Topical agents only, including topical antibiotics. Isotretinoin (Accutane) is not allowed.
Antiangular agents	N	N	Calcium agonists (e.g. diltiazem, nifedipine, verapamil) and beta blockers (e.g. carvedilol, propranolol, metoprolol) are excluded if used to treat angina.—
Antiarrhythmics	N	N	Amiodarone is excluded.
Antiasthma agents	Y	N	—
Antibiotics	Y	Y	Chronic use of topical antibiotics for acne is allowed, except for the MAOI linezolid (Zyvox) and isoniazid, which are not allowed. Erythromycin, clarithromycin, rifampin, and azithromycin are excluded.
Anticoagulants	N	N	Common drugs include: Warfarin (Coumadin) is not allowed. Antiplatelet agents are allowed (see “Antiplatelets”).
Anticholinergics	Y	Y	Except for scopolamine, which is not allowed.
Anticonvulsants	N	Y ^b	Gabapentin, and pregabalin are allowed. Other anticonvulsants are not allowed, including lamotrigine and carbamazepine.

Drug Name or Class	Episodic Use (PRN)	Chronic Use	Restrictions/Comments
Antidepressants	N	Y ^b	Monoamine oxidase inhibitors (which may have unknown drug-drug interactions) are excluded. Concomitant use of trazodone (up to 200mg daily), nefazodone or duloxetine are allowed. No dose changes are allowed during the study.
Antidiarrheal preparations	Y	N	Only loperamide HCl (Imodium), bismuth subsalicylate (Pepto-Bismol), and kaolin preparations are allowed.
Antifungals, systemic	N	N	
Antifungals, topical	Y	Y	
Antihistamines	Y	Y	The use of combinations containing pseudoephedrine or phenylephrine is not allowed. Combination products containing the word nighttime or are specifically marketed for before sleep routinely include an antihistamine and are not allowed. Combination products ending in “-D” routinely contain a stimulant such as phenylephrine, and the appropriate limits above apply to them. (See “Cough and Cold Preparations” for combination products.)
Antihypertensives	N	Y	Diltiazem, verapamil are excluded
Anti-impotence medications	Y	Y	—
Anti-inflammatory drugs	Y	N	Indomethacin (Indocin) and systemic corticosteroids are not allowed for PRN or chronic use. NSAID use is exclusionary.
Antimigraine	N	N	Common one includes: Triptans not allowed.

Drug Name or Class	Episodic Use (PRN)	Chronic Use	Restrictions/Comments
Antinauseants/ Antiemetics	Y	N	Phosphoric acid preparations (Emetrol, Emecheck), bismuth subsalicylate (Pepto-Bismol), cola syrup, 5-HT ₃ receptor antagonists (e.g., ondansetron), and prokinetic agents (metoclopramide) are allowed only for PRN. Scopolamine is not allowed for PRN or chronic use (see section on antihistamines).
Antineoplastics/ Immunosuppressant agents	N	N	Common drugs include: Interferons, methotrexate, and other immunosuppressant agents are not allowed. Call MGH CTNI for approval for certain cases in cancer remission maintaining therapy.
Antiobesity/ Appetite suppressants	N	N	Common drugs include: OTC Alli (Xenical), sibutramine (Meridia), and phentermine (Adipex-P and others) are not allowed.
Antiplatelet agents	N	Y ^b	Aspirin (maximum 325 mg/day) and clopidogrel (Plavix) are allowed. Note that use of an SSRI or of a triple uptake inhibitor may increase bleeding times and possibly prothrombin times.
Antipsoriatic treatments	Y	Y	Only topical agents are allowed. Acitretin (Soriatane) is not allowed.
Antipsychotics	N	N	—
Antismoking medications	N	N	Common drugs include: Varenicline (Chantix) is not allowed. Chronic nicotine replacement may be allowed in certain cases after review with MGH CTNI.

Drug Name or Class	Episodic Use (PRN)	Chronic Use	Restrictions/Comments
Antiviral agents	Y	Y	
Only oral or topical agents are allowed.
 
Only acyclovir, famciclovir, valacyclovir, penciclovir, docosanol, trifluridine, and vidarabine are allowed.
 
Amantadine, rimantadine, indinavir, nelfinavir, ritonavir, saquinavir are not allowed. Tamiflu (oseltamivir phosphate), and Relenza (zanamivir) inhalants are permitted for influenza prophylaxis but use is limited to a 7- to 14-day course in accordance with prescribing information.
 
Interferons are not allowed. Boceprevir (Victrelis®) is not allowed.

Anxiolytics	N	Y	Chronic, stable treatment with benzodiazepines is allowed. Stable in dosing at least four weeks prior to randomization is required.
Barbiturates	N	N	
Benign prostatic hyperplasia treatments	N	Y ^b	Male patients who have symptoms of obstructed voiding should not be included in the study. Surgically or medically treated patients must be asymptomatic and receiving a stable dosage of allowed medications (α -1 blockers, finasteride, or dutasteride) for 1 month before screening.
Buspirone	N	Y	Stable in dosing at least four weeks prior to randomization is allowed.
Cough/cold preparations	Y	N	Use of cough and cold preparations containing pseudoephedrine or dextromethorphan is not allowed, as are those containing phenylephrine. Combination products ending in “-D” routinely contain a stimulant such as phenylephrine, and the appropriate limits apply to them. (See “Antihistamines”.)
Diuretics	Y	Y ^b	Episodic use of diuretics is restricted to treatment of premenstrual symptoms. For chronic use, medication and dosage should be stable for 1 month before screening.

Drug Name or Class	Episodic Use (PRN)	Chronic Use	Restrictions/Comments
Dopaminergics	N	Y	Common drugs include: Dopamine agonists for restless leg syndrome are allowed for chronic use.
Gastrointestinal: • H ₂ -blockers/ • proton pump inhibitors/ • prokinetic agents	Y	Y	Cimetidine (Tagamet), metoclopramide, omeprazole and pantoprazole are not allowed within 7 days of Baseline.
Hormonal (noncontraceptive) therapies	N	Y	See below.
Hormone suppressants	N	Y ^b	Only finasteride (Proscar) and dutasteride (Avodart) are allowed for chronic use. Bromocriptine (Cycloset, Parlodel) is not allowed
Hormones: reproductive	N	Y	Systemic hormonal contraceptives (oral contraceptives of estrogen and progestin combinations, depot injections such as Depo-Provera, the contraceptive implant Implanon, or transdermally delivered contraceptives such as Ortho Evra) are allowed
Hormones: thyroid	N	Y	Thyroid hormone replacement is allowed (dosage of thyroid medication should be stable for 3 months before screening).
Hypoglycemic agents	N	Y	Oral and injectable hypoglycemic agents are allowed. Insulin is not allowed
Hypolipidemics	N	Y ^b	Common drugs includes: Ezetimibe (Zetia) is allowed for chronic use.
Hypolipidemics: bile acid sequestrants	N	N	—
Hypolipidemics: fibrates	N	Y ^b	Common drugs include: Gemfibrozil and fenofibrate are allowed for chronic use.
Hypolipidemics: niacin	N	N	Common drugs include: Oral niacin and niacinamide are not allowed
Hypolipidemics: statins	N	Y ^b	Lovastatin, simvastatin, pravastatin, fluvastatin, and rosuvastatin are allowed

Drug Name or Class	Episodic Use (PRN)	Chronic Use	Restrictions/Comments
Laxatives	Y	Y ^a	Only fiber-based products and docusate sodium (Colace) are allowed
Lithium	N	Y	Stable in dosing at least four weeks prior to randomization is allowed.
Muscle relaxants	N	N	—
NMDA receptor antagonist	N	N	Common drugs include: Memantine is not allowed.
Opioid agonists/analgesics (e.g., codeine, hydrocodone, methadone, morphine, maperidine, propoxyphene) and antagonists (e.g., naltrexone, naloxone, nalmefene)	Y	N	Intermittent use allowed, if the following criteria are met: 
 use has been ongoing for at least 4 weeks prior to Screening, frequency is no more than 4 days/week, and no dosing within 24 hours of a study visit.
Proton pump inhibitors or H2 receptor blockers	Y	Y	—
Sedatives/hypnotics	N	Y	Ongoing, stable hypnotic therapy (e.g., zolpidem, zaleplon, benzodiazepine hypnotics, and low-dose trazodone 50-200mg) will be allowed during the study. Eszopiclone is not allowed.
Steroids/systemic	Y	N	Systemic steroid treatment will be allowed only for medical emergencies, such as severe allergic reactions
Steroids/topical and inhalant	Y	Y	—
Steroids/intra-articular	N	N	—

Drug Name or Class	Episodic Use (PRN)	Chronic Use	Restrictions/Comments
Stimulants	N	Y	Chronic use allowed if taken for at least 12 weeks and at a stable dose for 4 weeks. The use of combinations containing pseudoephedrine or phenylephrine is not allowed.
Supplement and herbals	N	N	The following are the only exclusionary supplements/herbals: St. John's Wort, garlic, chamomile, grapefruit and pineapple juice
Vaccines	Y	NA	—

a *If being taken prior to enrolling in the study.*

b *If being taken for at least 3 months prior to enrolling in the study and the dose has been stable for at least 1 month.*

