23. Female has a positive pregnancy test at the Screening or Baseline Visit, is planning to become pregnant, or is breastfeeding.
24. Has ongoing litigation for workers' compensation.
25. Known diagnosis of long QT syndrome.
26. Male has a QRS interval ≥ 120 ms *and* QTcF ≥ 460 ms OR female has a QRS interval ≥ 120 ms *and* QTcF ≥ 480 ms at Screening.
27. Has moderate to severe congestive heart failure (New York Heart Association [NYHA] class III and class IV).
28. Has a history of symptomatic cardiovascular disease.
29. Current therapy with any immunosuppressive therapy, including corticosteroids (>5 mg/day of prednisone).

30. Moderate to severe hepatic impairment at the Screening Visit, as defined by any of the following:

- AST **and** ALT values that are ≥ 1.5 times ULN

31. Moderate to severe renal impairment at the Screening Visit, as defined by either:

- An estimated glomerular filtration rate [eGFR] < 45 mL/min; or
- A serum creatinine level > 1.3 mg/dL.

32. Use of CYP3A4 inhibitors (e.g., grapefruit juice, pantoprazole) or CYP3A4 inducers (e.g., omeprazole, carbamazepine, rifampin, St. John's wort) within 7 days prior to the Baseline Visit. Please see Appendix III. Concomitant Medications.

33. Use of CYP2C9 inhibitors (e.g., amiodarone, fluconazole) or CYP2C9 inducers (e.g. carbamazepine, rifampin, St. John's wort) within 7 days prior to the Baseline Visit. Please see Appendix III. Concomitant Medications.

34. Use of P-glycoprotein inhibitors (e.g., atorvastatin, azithromycin, carvedilol) within 7 days prior to the Baseline Visit or any time during study participation, unless taken for at least 3 months prior and at a stable dose for at least 1 month prior to the Baseline Visit. Please see Appendix III. Concomitant Medications.

35. Is classified as a poor metabolizer via the CYP2C9 pathway as determined by genetic testing (CYP2C9 genotyping).

36. Has clinically significant pulmonary disease such that chronic, daily use of medical treatment is required (e.g. COPD, asthma).

37. Has any of the following blood counts:

- Monocyte count < 1 % of white blood cells (e.g., for WBC = 4,500/ μ L, exclude patient if monocyte count $< 0.01 * 4,500$ or 45/ μ L; for WBC = 11,000/ μ L, exclude patient if monocyte count $< 0.01 * 11,000$ or 110/ μ L)
- Platelet count, or
 - Females (sex at birth): $< 125,000/\mu$ L
 - Males (sex at birth): $< 150,000/\mu$ L
- Hemoglobin:
 - Females (sex at birth): < 11.5 grams/dL
 - Males (sex at birth): < 13.0 grams/dL

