The primary safety endpoint for the study is the following: Percent of adverse events and serious adverse events in the final 2 weeks of each treatment period. Vital signs (heart rate, blood pressure, etc.) will be obtained regularly throughout the study at the time of study visits. Height and weight will be collected during the screening period and at the subject's final study visit. Blood chemistry and hematology panels will also be obtained regularly at study visits. All ECGs will be documented by recording date, time, heart rate, QRS duration, PR interval, RR interval, QT, and QTcF on the eCRF. Paper strips will be maintained in the patient file. If indicated, additional ECG assessments can be made at the discretion of the investigator.

Because CNTX-6970 is metabolized by CYP2C9 and CYP3A4 (to a lesser extent), use of inhibitors and inducers of those two genes are excluded for the duration of participation in the trial. CYP2C9 genotyping will be used to exclude poor metabolizers. As a P-glycoprotein (P-gp) substrate, introduction of any new P-gp inhibitor is also exclusionary for the duration of study participation – P-gp use must have been chronic for at least 3 months and stable for at least 1 month prior to Baseline. Additionally, until more is known about the hepatic metabolism and renal excretion of CNTX-6970, individuals with moderate to severe impairment in hepatic or renal functioning will be excluded from participation.

ECGs will be done at each in-clinic visit to assess heart health. Urine dipstick/urinalysis and liver functioning tests (AST, ALT, GGT, total bilirubin, direct bilirubin, ALK phosphatase) will be collected at each in-clinic visit to monitor the subject's health throughout the study.

F.3. Discontinuation

F.3.1. Discontinuation of Subjects

In accordance with the Declaration of Helsinki and other applicable regulations, subjects have the right to withdraw from the study at any time, and for any reason, without prejudice to their future medical care. Subjects may be discontinued or withdrawn from the study for any of the following reasons:

- Serious adverse event.
- The investigator determines that continuation in the study would be detrimental to a subject's well-being, including criteria under F.3.1.1
- Subject fails to comply with protocol requirements.
- Subject misses more than 6 consecutive doses of study medication.
- Subject is lost to follow-up.
- Subject becomes pregnant.

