Drug-drug interactions (DDI) resulting from inhibition of transporters or cytochrome P450 (CYP) are unlikely to occur in humans; the mean maximum plasma concentration (Cmax) in humans after a single oral dose of 600mg is at least 18-fold lower than the concentration at 50% inhibition for the transporters studied. Additionally, CNTX-6970 was predominantly metabolized by CYP2C9 with a minor contribution of CYP3A4. Concomitant use of CYP2C9 and CYP3A4 inducers and inhibitors is prohibited within 7 days of Baseline and during participation in this trial. P-glycoprotein inhibitors are also prohibited, as CNTX-6970 is a P-glycoprotein substrate, unless use has been chronic for at least 3 months and stable for at least 1 month prior to Baseline.

G.5. Analgesic and Rescue Medications

Subjects may continue use of tramadol, gabapentin, duloxetine, pregabalin, milnacipran, or a tricyclic antidepressant, if prescribed for pain and use is chronic for at least 12 weeks and at a stable dose for at least 4 weeks prior to Screening. Other continuous, chronic analgesic treatments are exclusionary.

Some medications that may impact pain are used to treat non-pain indications. For this trial, continuous use of such medications, e.g. duloxetine for depression, may be continued throughout study participation, if the dose has been stable for at least 12 weeks prior to Screening. Additionally, continued use of low-dose aspirin for heart disease prophylaxis is allowed.

Starting with the first visit, the only allowable analgesic rescue medications that can be taken for pain are acetaminophen and opioids (see Appendix III and MOP for additional details, including maximum daily dosing). Intermittent use of opioids must have started at least four weeks prior to Screening; introduction of new opioid treatment during the study is prohibited. The amount of rescue medication(s) taken each day will be recorded by the subject in the NEForm app.

G.6. Concomitant Medications

For a full list of concomitant medications and their restrictions for use, please see Appendix III: Concomitant Medications.

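### Protocol: omeprazole or pantoprazole after Baseline is permitted by the Appendix III table but prohibited by G.4 and F.2.7 read with exclusion 32

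*Protocol*

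**What the plan says.** Five places in the protocol bear on these drugs.

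- **E.4.2, exclusion 32** excludes "Use of CYP3A4 inhibitors (e.g., grapefruit juice, pantoprazole) or CYP3A4 inducers (e.g., omeprazole" among other examples. Its window is "within 7 days prior to the Baseline Visit. Please see Appendix III. Concomitant Medications", so it ends at Baseline and sends the site to the appendix.
- **G.4 Possible Drug Interactions**: "Concomitant use of CYP2C9 and CYP3A4 inducers and inhibitors is prohibited within 7 days of Baseline and during participation in this trial".
- **F.2.7 Safety Measures**, speaking of CYP2C9 and CYP3A4: "use of inhibitors and inducers of those two genes are excluded for the duration of participation in the trial".
- **Appendix III, gastrointestinal row** (H2-blockers, proton pump inhibitors and prokinetic agents; Y for episodic and Y for chronic use): "Cimetidine (Tagamet), metoclopramide, omeprazole and pantoprazole are not allowed within 7 days of Baseline".
- **Appendix III, separate row** headed "Proton pump inhibitors or H2 receptor blockers": Y and Y, with a dash in the comments column.

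The consequences are set elsewhere. The opening of Appendix III says that a subject who takes a prohibited drug is discontinued unless stopping would carry too great a medical risk, and that the event is a major protocol deviation whether or not the subject stays. G.6 says that patients who need an excluded drug are discontinued. For therapy that interferes with drug metabolism or transport, G.6.1 allows exceptions that the investigator documents and discusses with the Medical Monitor.

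**The concern.** Exclusion 32 and G.6 direct sites to Appendix III for medication questions, and its table is the permissive text. A site working from that table has no reason to act when a randomized patient starts omeprazole or pantoprazole. A site working from G.4 or F.2.7 would report a major deviation and move to discontinue. Both would be following the protocol in good faith.

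Two things are at stake. The first is who stays in. The SAP's sequences are drug, placebo, placebo, drug and the reverse pattern. A patient withdrawn at the end of the first period has received only one treatment and gives no within-patient comparison. The second is what the retained patients were exposed to. A drug that the protocol itself treats as a CYP3A4 inhibitor or inducer could be present in one of a patient's two active periods and absent in the other. Deviation counts would also differ between sites for identical events.

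**Working it through.** No sample size, rate or formula is involved, so the check is to apply each rule to the same patient.

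**Step 1. Are the two drugs in the prohibited class?** Exclusion 32 gives pantoprazole as an example of a CYP3A4 inhibitor and omeprazole as an example of a CYP3A4 inducer. G.4 and F.2.7 prohibit CYP3A4 inhibitors and inducers as a class. No single section both names the drugs and covers the whole trial. The conflict appears when the protocol's own classification in exclusion 32 is carried into G.4 and F.2.7.

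**Step 2. Apply each rule to a randomized patient who takes omeprazole or pantoprazole at, say, Week 9.**

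| Source | Result after Baseline |
|---|---|
| Exclusion 32 | Silent (window ends at Baseline) |
| Appendix III, gastrointestinal row | Allowed (outside the 7-day window) |
| Appendix III, row with no comment | Allowed |
| G.4 | Prohibited |
| F.2.7 | Prohibited |
| G.6 and opening of Appendix III | Discontinue if prohibited, subject to exceptions; Appendix III makes it a major deviation either way |

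Both table rows keep the patient. G.4 and F.2.7 put the same patient on the route to discontinuation.

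**Step 3. Apply the rules in the 7 days before Baseline.** Exclusion 32, G.4 and the gastrointestinal row all bar the two drugs. Only the row with no comment lacks the limit. It can be read as a general class entry that the drug-specific row qualifies, so the duplication is untidy but need not be a contradiction. The real dispute is the period after Baseline.

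**Step 4. Does other wording settle the intent?** Exclusion 34, on P-glycoprotein inhibitors, adds "or any time during study participation, unless taken for at least 3 months prior". Exclusion 32 has no such words. That could mean that a Baseline-only rule was intended for CYP3A4, but G.4 and F.2.7 say the opposite. The documents do not settle it, and this review does not say which rule is clinically right.

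**The case against.** The strongest reply has three parts.

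*A central contact exists.* G.6 and Appendix III send medication questions to the Medical Monitor, G.6.1 allows documented exceptions, and Appendix III has its medical-risk exception. This stands to the extent that discontinuation is not automatic. It does not cure the conflict, because those routes open only once someone sees a prohibited drug or a question to ask. A site reading the table sees neither.

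*CYP3A4 is a minor pathway.* A.1 and G.4 say that metabolism is mainly by CYP2C9. This stands and limits what can be said about exposure. It leaves the conflict over retention and deviation reporting untouched.

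*No section both names the drugs and says throughout.* This is true, and it limits how the point may be stated. The class rule and the classification still come from the same protocol.

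A reader might also infer more than the documents support:

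- *That all proton pump inhibitors and H2 blockers are caught.* Exclusion 32 classifies only omeprazole and pantoprazole from these groups, so the conflict is shown for those two.
- *That the metoclopramide entries contradict each other.* The gastrointestinal row bars it within 7 days of Baseline, and the antinauseant row allows it only as needed. A site can follow both by confining as-needed use to the time outside that window. The documents do not call it a CYP3A4 or CYP2C9 inhibitor or inducer.
- *That a share of completers is lost.* One could set a few assumed cases against the 29 completers in SAP Section 6. The case count would be a guess, and those patients might not have completed anyway, since the SAP assumes 15% early termination per period. The 29 is also a conservative completers-only figure, because the analysis uses all data up to discontinuation.

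**Conclusion.** The conflict is in the current text and holds for omeprazole and pantoprazole taken after the Baseline window. The Appendix III table permits them. G.4 and F.2.7, read with exclusion 32, make their use a major deviation leading to discontinuation, subject to the medical-risk exception and the documented-exception route. The conclusion rests on one step of reading: that the class prohibited in G.4 and F.2.7 includes the drugs that exclusion 32 lists as members of it.

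The size is unknown. The documents give no rate of use and no change in CNTX-6970 exposure with either drug, so no percentage should be attached and no effect on power or bias is shown. The point still deserves correction, because it decides whether a patient is kept and how the event is reported, and it is cheap to settle.

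**What to change.** Reconcile exclusion 32, F.2.7, G.4 and the two Appendix III rows into one statement of whether omeprazole and pantoprazole are prohibited and for what period. The sponsor's clinical team must decide the content. Merge the two rows so that the class appears once, and have exclusion 32, F.2.7 and G.4 refer to that entry. Apply the same statement to eligibility, deviation reporting and discontinuation, and tell sites in a memo. As a clarity point only, cross-reference the metoclopramide entries in the antinauseant and gastrointestinal rows.

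The cost is an administrative protocol amendment and the memo. No change to the design, sample size or SAP models is needed.
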